$253 \leq \text{Study Day} \leq 308$	$253 \leq \text{Study Day} \leq 322$	Week 40
$295 \leq \text{Study Day} \leq 378$	$295 \leq \text{Study Day} \leq 378$	Week 48
$365 \leq \text{Study Day} \leq 420$	$365 \leq \text{Study Day} \leq 434$	Week 56
$421 \leq \text{Study Day} \leq 476$	$421 \leq \text{Study Day} \leq 490$	Week 64
$477 \leq \text{Study Day} \leq 532$	$477 \leq \text{Study Day} \leq 546$	Week 72
$533 \leq \text{Study Day} \leq 588$	$533 \leq \text{Study Day} \leq 602$	Week 80
$589 \leq \text{Study Day} \leq 644$	$589 \leq \text{Study Day} \leq 658$	Week 88
$631 \leq \text{Study Day} \leq 714$	$631 \leq \text{Study Day} \leq 714$	Week 96

NOTES:

- For post-baseline visits (i.e. Week 4 and afterwards), apply Snapshot analysis windows only to viral load data that is on-treatment (per Table 16) within the Maintenance Phase (per Table 14).
- An on-treatment viral load assessment may be assigned to more than one snapshot analysis window, e.g. on-treatment assessment taken on Study Day 300 will be in both Week 40 and Week 48.

a. ± 6 Week window is always used at key analysis timepoints (Week 48 and Week 96). For analysis timepoint of Week 24, if no viral load data in default window, expand to ± 6 Week window, i.e. ($127 \leq \text{Study Day} \leq 210$) in Week 24 IDMC and Week 24 Analyses, and expand upper bound to +6 weeks in all other analyses.

Table 11 Assessment Windows for Summaries of Long-Term Follow Up Phase Data for Participants Who Received At Least One Injection of CAB+RPV and Permanently Discontinued Study Treatment

Analysis Window	Analysis Timepoint	Target Study Day of Window
$1 \leq \text{LTFU Study Day} \leq 63$	LTFU Month 1/WD ^[a]	30
$64 \leq \text{LTFU Study Day} \leq 135$	LTFU Month 3	90
$136 \leq \text{LTFU Study Day} \leq 225$	LTFU Month 6	180
$226 \leq \text{LTFU Study Day} \leq 315$	LTFU Month 9	270
$316 \leq \text{LTFU Study Day} \leq 405$	LTFU Month 12	360
$(30*m - 44) \leq \text{LTFU Study Day} \leq (30*m + 45)$	LTFU Month m m = 15, 18, 21, ...	7*m

NOTES:

- An assessment may be assigned to both LTFU and maintenance/extension phases.

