15.4.2. Treatment State

Within each treatment study phase (i.e. Maintenance and Extension—based on assignment of study phase described in Section [15.4.1](#)), only those assessments which occur within the ranges shown in [Table 16](#) will be considered ‘on-treatment’ for the given phase. No treatment states will be assigned to medications.

Table 16 Treatment State within Study Phases^b

Study Phase ^a	Treatment State	Date Range
Screening	Pre-treatment	All assessments/events within the phase
Maintenance	On-treatment	Q8W arm: Date ≤ max (Date of Last Injection + 63, Date of Last Dose of Oral CAB+RPV + 1)
		Q4W arm: Date ≤ max (Date of Last Injection + 35, Date of Last Dose of Oral CAB+RPV + 1)
	Post-treatment	Q8W arm: Date > max (Date of Last Injection + 63, Date of Last Dose of Oral CAB+RPV + 1)
		Q4W arm: Date > max (Date of Last Injection + 35, Date of Last Dose of Oral CAB+RPV + 1)
Extension	On-treatment	Q8W arm: Date ≤ max (Date of Last Injection + 63, Date of Last Dose of Oral CAB+RPV + 1)
		Q4W arm: Date ≤ max (Date of Last Injection + 35, Date of Last Dose of Oral CAB+RPV + 1)
	Post-treatment	Q8W arm: Date > max (Date of Last Injection + 63, Date of Last Dose of Oral CAB+RPV + 1)
		Q4W arm: Date > max (Date of Last Injection + 35, Date of Last Dose of Oral CAB+RPV + 1)
Long-term Follow-up	On-treatment	Q8W arm: Date ≤ min (LTFU ART start date, max (Date of Last Injection + 63, Date of Last Dose of Oral CAB+RPV + 1))
		Q4W arm: Date ≤ min (LTFU ART start date, max (Date of Last Injection + 35, Date of Last Dose of Oral CAB+RPV + 1))
	Post-treatment	Q8W arm: Date > min (LTFU ART start date, max (Date of Last Injection + 63, Date of Last Dose of Oral CAB+RPV + 1))
		Q4W: Date > min (LTFU ART start date, max (Date of Last Injection + 35, Date of Last Dose of Oral CAB+RPV + 1))
NOTE:		

 • Date = Assessment/Start Date. a. Treatment State is determined after data has been assigned to the study phases as defined in Section 15.4.1. b. Last injection and/or last dose of oral CAB+RPV are only applied to participants who permanently discontinued the study treatment. The assessments for participants who did not permanently discontinue the study treatment will be considered 'On-treatment'. For participants continuing into extension phase, all data assigned to maintenance phase per Section 15.4.1 will be considered 'On-treatment'. 		

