 - CDC Stage III at Baseline to new CDC Stage III event;
 - CDC Stage I, II, III at Baseline to Death.

Please refer to Protocol (Appendix 4: CDC Classification for HIV-1 Infection) for defining Stage.

- For the purpose of analysis, the CDC at Baseline and at post-baseline during Maintenance Phase will be derived as below:
 - At Baseline, the 'Baseline CDC stage' for each participant was assessed by investigator and recorded in the eCRF. However, for the analysis, Baseline CDC stage will be rederived based Baseline CD4+ values as well as whether any HIV-associated/AIDS-defining conditions present at baseline per the Criteria's thresholds (Appendix 4 in Protocol).
 - To analyse disease progression, the most advanced post-baseline CDC stage within the period of interest (e.g. Maintenance Phase) will be derived based on the occurrences of new AIDS-defining conditions (please refer to Appendix 4 in Protocol for the list of AIDS-defining Conditions) as well as the nadir value of post-baseline CD4+.
 - For example, if a participant with CDC 'Stage I' at Baseline had the lowest Maintenance Phase CD4+ =120 cell/mm³ without new AIDS-defining conditions, then HIV disease progression for this participant during the Maintenance Phase would be considered as 'CDC stage I at Baseline to CDC stage III'.
 - If a participant with CDC 'Stage II' at Baseline had the lowest Maintenance Phase CD4+ =220 cell/mm³ AND had at least one new AIDS-defining condition, then HIV disease progression for this participant during the Maintenance Phase would be considered as 'CDC stage II at Baseline to CDC stage III'.

Delay in IP Injection

- For participants on the Q4W arm, IM dosing is expected to occur every 4 weeks from Week 4B onwards for those transitioning from SOC (i.e. those requiring oral lead-in) and from Day 1 onwards for those transitioning from CAB+RPV Q4W in ATLAS (i.e. those not requiring oral lead-in). The Delay in IP injection (days) will be calculated as:
 Delay in IP Injection (days) = Injection date - date of preceding injection - 28 days
- For participants on the Q8W arm, IM dosing is expected to occur at Week 4B and then every 8 weeks from Week 8 onwards for those transitioning from SOC (i.e. those requiring oral lead-in) and every 8 weeks from Day 1 for those transitioning from CAB+RPV Q4W (i.e. those not requiring oral lead-in) in ATLAS.

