 - For participants transitioning from SOC on the Q8W arm, if the preceding injection occurs at Week 4B, the Delay in IP injection (days) will be calculated as:
 Delay in IP Injection (days) = Date of Week 8 injection - date of Week 4B injection - 28 days
 - For participants transitioning from SOC on the Q8W arm, if the preceding injection occurs at a visit later than Week 4B, the Delay in IP injection (days) will be calculated as:
 Delay in IP Injection (days) = Injection date - date of preceding injection - 56 days
 - For participants transitioning from CAB+RPV Q4W in ATLAS on the Q8W arm, the Delay in

IP injection (days) will be calculated as:
 Delay in IP Injection (days) = Injection date - date of preceding injection - 56 days

- Delay in IP injection will be grouped into: ≤1, 2-3, 4-7, >7 days.
- The proportion of participants with HIV-1 RNA ≥50 c/mL at Week 48 (Snapshot) will be summarized by last delay in IP Injection. The last delay in IP injection will be the delay in IP injection at Week 48, or the delay in last IP injection prior to Week 48 if a participant did not receive Week 48 injection (i.e. missing visit or withdrawal).

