
Timeliness of Injections relative to Date of Projected Dosing Visits are assessed by using "actual injection visit date - projected visit date from first injection". The injections of interest in adherence analysis are those after first injection. For participants requiring the oral CAB+RPV lead-in, the first injection is planned to be taken at Week 4B. For participants not requiring the oral CAB+RPV lead-in, the first injection is planned to be taken at Baseline/Day 1. Each injection visit is counted only once. Individual CAB and RPV injections administered at the same visit are not counted twice. "Extra" unscheduled injections are excluded from all derivations. For example, if during a scheduled visit a participant receives 1 ml of injection instead of 2 ml due to a dosing error, but this participant returns one week later for the remaining 1 ml injection, then the additional visit is excluded. If a participant receives an extra injection at an unscheduled visit by mistake, this visit will also be excluded.
 
The categories of Timeliness of Injections relative to Date of Projected Dosing Visits for summary are listed below:
 
 < -14 days -14 to -8 days -7 to -4 days -3 to -2 days -1 0 day 1 2 to 3 days 4 to 7 days 8 to 14 days >14 days Missed Injection without Oral Bridging Missed Injection with Oral Bridging
Columbia Suicide Severity Rating Scale (C-SSRS)

 • Missing data will not have any imputation performed (Nilsson et al, 2013).

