2.13	2.13	NA	Intent-to-Treat Exposed	201584/primary_01/T2.11	Proportion of Subjects with Plasma HIV-1 RNA >=50 c/mL by Visit (Maintenance Phase) – Snapshot Analysis		W48, W96
2.14	2.14	NA	Intent-to-Treat Exposed	201584/primary_01/T2.12	Proportion of Subjects with Plasma HIV-1 RNA >=50 c/mL by Subgroup and Visit (Maintenance Phase) – Snapshot Analysis		W48, W96
2.15	2.15	NA	Intent-to-Treat Exposed	201584/primary_01/T2.15	Proportion of Subjects with Plasma HIV-1 RNA <50 c/mL by Visit (Maintenance Phase) – Snapshot Analysis		W48, W96

Efficacy Tables							
No. in W48	No. in W96	No. in EOS	Population	IDSL / Example Shell	Title	Programming Notes	Deliverable
2.16	2.16	NA	Intent-to-Treat Exposed	201584/primary_01/T2.16	Proportion of Subjects with Plasma HIV-1 RNA <50 c/mL by Subgroup and Visit (Maintenance Phase) – Snapshot Analysis		W48, W96
2.17	2.17	NA	Intent-to-Treat Exposed	201584/primary_01/T2.17	Proportion of Subjects with Plasma HIV-1 RNA <200 c/mL by Visit (Maintenance Phase) – Snapshot Analysis		W48, W96
2.18	2.18	NA	Intent-to-Treat Exposed	201584/primary_01/T2.17	Proportion of Subjects with Plasma HIV-1 RNA ≥200 c/mL by Visit (Maintenance Phase) – Snapshot Analysis	Adjust column headers as appropriate. Keep one decimal place for proportion.	W48, W96
2.19	2.19	NA	Intent-to-Treat Exposed	Shell EFF_T1	Summary of Kaplan-Meier Estimates of Proportion of Subjects Without Confirmed Virologic Failure at Week 48 - Treatment Related Discontinuation = Failure	Adjust the row labels and footnotes as appropriate. For WK96, replace 'Week 48' with 'Week96' in title.	W48, W96
2.20	2.20	NA	Intent-to-Treat Exposed	Shell EFF_T2	Summary of Kaplan-Meier Estimates of Proportion of Subjects Without Confirmed Virologic Failure at Week 48 - Efficacy Related Discontinuation = Failure	Adjust the row labels and footnotes as appropriate. For WK96, replace 'Week 48' with 'Week96' in title.	W48, W96
2.21	2.21	NA	Intent-to-Treat Exposed	201585/primary_02/T2.19	Proportion of Subjects with HIV-1 RNA ≥50 c/mL at Week 48 (Snapshot) by Last Delay in IP Injection (Maintenance Phase)	Display both arms. Change the footnote to 'The last delay in IP injection will be the delay in IP injection at Week 48, or the delay in last IP injection prior to Week 48 if a participant did not receive Week 48 injection (i.e. missing visit or withdrawal)..'. For WK96, replace 'Week 48' with 'Week96' in title.	W48, W96

Efficacy Tables							

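### In the table of Week 48 failure by injection delay, a participant still on study whose Week 48 injection was missed and unbridged can be graded '≤1 day' late, because the previous injection's delay is used

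*SAP*

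**What the plan says.** Section 15.6.3 of the SAP (Delay in IP Injection) defines delay between two injections that were both given. For Q4W it is "Delay in IP Injection (days) = Injection date - date of preceding injection - 28 days". For Q8W, after the first post-lead-in interval, it is "Delay in IP Injection (days) = Injection date - date of preceding injection - 56 days". The groups are fixed: "Delay in IP injection will be grouped into: ≤1, 2-3, 4-7, >7 days".

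The Week 48 Snapshot failure proportion is then summarised by the last delay. A participant without a Week 48 injection, whether from a missed visit or a withdrawal, takes "the delay in last IP injection prior to Week 48 if a participant did not receive Week 48 injection". The programming note for Table 2.21 in Section 15.14.5.2 repeats this: "The last delay in IP injection will be the delay in IP injection at Week 48, or the delay in last IP injection". The same display is reused at Week 96. The only change stated there is to the title, so I take the rule to carry over.

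Two other parts of the SAP bear on this:

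- Table 16, note b (Section 15.4.2) puts no limit on time since injection for people still on study: assessments for "participants who did not permanently discontinue the study treatment will be considered 'On-treatment".
- The adherence summary in Section 15.6.4 gives missed injections their own categories, one of them "Missed Injection without Oral Bridging" and the other its counterpart with bridging.

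**The concern.** For a participant who received the Week 48 injection, the table grades the interval ending at that injection. For one who did not, it grades an earlier interval that ended on its own terms. One column therefore holds two different exposures, and their order can reverse: an injection given weeks late is graded '>7 days', while one never given can be graded '≤1 day'.

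Table 2.21 is the only planned display that relates injection delay to HIV-1 RNA ≥50 c/mL. A reader will take the '≤1 day' group as participants dosed on schedule up to the endpoint. Under this rule it can include participants with an open, unbridged gap at the viral load that decides their outcome.

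**Working it through.** No sample size, power or error rate depends on this rule, so there is no planned figure to reproduce. The check applies the SAP's own formulas to scheduled dates.

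**Inputs**
- Target day for week w is 7w + 1 (Section 15.3.1): Week 32 = Day 225, Week 40 = Day 281, Week 44 = Day 309, Week 48 = Day 337, Week 52 = Day 365, Week 56 = Day 393.
- Week 48 Snapshot window: Study Days 295 to 378 (Table 10).
- Planned interval: 56 days (Q8W) or 28 days (Q4W) (Section 15.6.3).
- On-treatment limit after permanent discontinuation: last injection + 63 days (Q8W) or + 35 days (Q4W), unless later oral dosing extends it (Table 16).

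**Q8W, Week 40 injection on time**
- Week 48 injection given on Day 370: 370 − 281 − 56 = 33 days, group '>7'.
- Week 48 injection not given: the rule takes the Week 40 delay, 281 − 225 − 56 = 0, group '≤1'.
- Open excess at a viral load on Day v is v − 281 − 56 = v − 337. This is 0 on Day 337, 8 on Day 345 (so more than 7 from there on), and 41 on Day 378.

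**Q4W, Week 44 injection on time**
- Week 48 injection not given: the rule takes the Week 44 delay, 0, group '≤1'.
- Open excess at Day v is v − 309 − 28 = v − 337, the same as for Q8W: 8 on Day 345 and 41 on Day 378. The Day 378 figure requires that no injection was given by then, so the Week 52 injection (Day 365) was not given either. If the Week 52 injection was given on schedule, the gap closes at 365 − 309 − 28 = 28 days.

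**Permanently discontinued, no later oral dosing**
- Largest excess at a counted viral load: 63 − 56 = 7 days (Q8W) and 35 − 28 = 7 days (Q4W), group '4-7' at most.

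**A case the rule handles correctly**
- Q8W, Week 40 missed and Week 48 given on Day 337: 337 − 225 − 56 = 56 days, group '>7'.

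**Week 96**
- The window ends on Day 714 and Week 96 is Day 673. With Week 88 (Day 617, Q8W) or Week 92 (Day 645, Q4W) the last injection given and on time, the excess at Day 714 is 714 − 617 − 56 = 41 or 714 − 645 − 28 = 41. The position is the same.

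**The case against.** The case for leaving the rule alone has real weight.

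- **Withdrawals.** The on-treatment limit holds the excess at a counted viral load to 7 days. If someone stops after failing, the injection not given comes after the failure, and the delay before the last injection given is a sensible exposure. This stands, and is why withdrawals need separating from missed injections.
- **Opportunity.** In the Q8W schedule, viral load and injection fall at the same visit. The neighbouring scheduled viral loads, Week 40 (Day 281) and Week 56 (Day 393), are both outside the window. A Q8W participant who misses the Week 48 visit on these dates has no scheduled viral load in the window, so the 41-day case needs an unscheduled draw. This also stands. It makes the extreme case uncommon, not impossible: the schedule of activities itself provides for an unscheduled Week 48 retest within 4 weeks when the result exceeds 50 c/mL.
- **Oral bridging.** A missed injection covered by bridging is not an uncovered gap.
- **Reach.** The table is descriptive and carries no test. Missed injections are summarised in the adherence table, and exposure and viral load listings let individual cases be traced.

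A reader might also infer that the rule biases the table towards showing no effect of delay. The SAP does not support that. Under Section 15.9, a participant on study with no viral load in the window is classed as having no virologic data, not as ≥50 c/mL. If kept in the denominator, such participants enlarge the '≤1 day' group as non-failures and lower its failure proportion. Those with a late viral load could raise it. The SAP does not show which dominates.

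**Conclusion.** The point holds in a limited form, and it is minor. A participant still on study whose Week 48 injection was missed and unbridged can be placed in '≤1 day' while up to 41 days past the planned interval at a Day 378 viral load. Any viral load from Day 345 is more than 7 days past it. These figures assume scheduled dates, an on-time last injection (Week 40 for Q8W, Week 44 for Q4W) and no injection before the viral load. An injection given late enough is graded '>7 days', so the ordering of exposures can reverse.

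It would be too strong to say that the longest gaps are always counted as on time. Placement depends on whether the previous injection was within 1 day of schedule, and a missed injection followed by a given Week 48 injection is graded correctly. The SAP gives no count of affected participants, so no effect on the reported proportions can be computed. The primary non-inferiority analysis does not use the delay groups and is unaffected.

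**What to change.** In Section 15.6.3 and the Table 2.21 footnote, stop assigning the previous injection's delay to participants who did not receive the Week 48 injection. Show them in a separate row, 'Week 48 injection not received', split into:

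- missed without oral bridging,
- missed with oral bridging (the same split as in Section 15.6.4),
- withdrawn.

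Keep the four delay groups for participants who received the Week 48 injection. Apply the same rule at Week 96 and say so in the text. A separate row also accommodates participants with no viral load in the window, for whom a delay measured to the viral load date would be undefined.

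The cost is one derivation and one extra row, likely with small counts. The injection dates and bridging records are already used elsewhere in the SAP, so no new data are needed.

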15.6.4. Safety

Adverse Events																					
DAIDS Grading																					

 • Clinical adverse events will be graded based on the Division of AIDS Table for Grading the Severity of Adult and Pediatric Adverse Events Version 2.1, March 2017, as specified in the protocol Appendix 11.2. 																					
Potential QTc Interval Prolonging Events of Interest																					

Potential QTc Interval Prolonging Events of Interest will be identified based on Standardised MedDRA Query (SMQ) for Torsade de pointes/QT prolongation, broad (MedDRA). The terms per this reference are listed below.
 
  
 AE preferred term	
   
Electrocardiogram QT interval abnormal	
 
Electrocardiogram QT prolonged	
 
Long QT syndrome	
 
Long QT syndrome congenital	
 
Torsade de pointes	
 
Ventricular tachycardia	
 
Cardiac arrest	
 
Cardiac death	
 
Cardiac fibrillation	
 
Cardio-respiratory arrest	
 
Electrocardiogram repolarisation abnormality	
 
Electrocardiogram U wave inversion	
 
Electrocardiogram U wave present	
 
Electrocardiogram U-wave abnormality	
 
Loss of consciousness	
 
Sudden cardiac death	
 
Sudden death	
 
Syncope	
 
Ventricular arrhythmia	
 
Ventricular fibrillation	
  
	AE preferred term	Electrocardiogram QT interval abnormal	Electrocardiogram QT prolonged	Long QT syndrome	Long QT syndrome congenital	Torsade de pointes	Ventricular tachycardia	Cardiac arrest	Cardiac death	Cardiac fibrillation	Cardio-respiratory arrest	Electrocardiogram repolarisation abnormality	Electrocardiogram U wave inversion	Electrocardiogram U wave present	Electrocardiogram U-wave abnormality	Loss of consciousness	Sudden cardiac death	Sudden death	Syncope	Ventricular arrhythmia	Ventricular fibrillation
AE preferred term																					
Electrocardiogram QT interval abnormal																					
Electrocardiogram QT prolonged																					
Long QT syndrome																					
Long QT syndrome congenital																					
Torsade de pointes																					
Ventricular tachycardia																					
Cardiac arrest																					
Cardiac death																					
Cardiac fibrillation																					
Cardio-respiratory arrest																					
Electrocardiogram repolarisation abnormality																					
Electrocardiogram U wave inversion																					
Electrocardiogram U wave present																					
Electrocardiogram U-wave abnormality																					
Loss of consciousness																					
Sudden cardiac death																					
Sudden death																					
Syncope																					
Ventricular arrhythmia																					
Ventricular fibrillation																					

Adverse Events	
Ventricular flutter	
Ventricular tachyarrhythmia	

Laboratory Parameters

 If a laboratory value which is expected to have a numeric value for summary purposes, has a non-detectable level reported in the database, where the numeric value is missing, but typically a character value starting with '<x' or '>x' (or indicated as less than x or greater than x in the comment field) is present, the number of significant digits in the observed values will be used to determine how much to add or subtract in order to impute the corresponding numeric value. If a character value starting with "<=x", then the numeric value will be x. 
 Example 1: 2 Significant Digits = '< x ' becomes x - 0.01 Example 2: 1 Significant Digit = '> x' or '>=x' becomes x + 0.1 Example 3: 0 Significant Digits = '< x' becomes x - 1
Estimate of Glomerular Filtration Rate (GFR) (Levey AI et al, 2012)

 Chronic Kidney Disease Epidemiology Collaboration (CKD-EPI) equation [Levey et al, 2012] will be used by the central laboratory to provide an estimate of GFR, in mL/min per 1.73 m², as follows: $GFR = 141 \times \min\left(\frac{CRT_{mg/dL}}{\kappa}, 1\right)^\alpha \times \max\left(\frac{CRT_{mg/dL}}{\kappa}, 1\right)^{-1.209} \times 0.993^{Age} \times [1.018 \text{ if Female}] \times [1.159 \text{ if Black}]$ 
where age (in years) is at time of assessment, $\kappa = 0.7$ if female or 0.9 if male, $\alpha = -0.329$ if female and -0.411 if male, $\min()$ indicates the minimum of CRT/κ or 1, $\max()$ indicates the maximum of CRT/κ or 1, and CRTmg/dL is serum creatinine concentration in mg/dL. The serum creatinine concentration in mg/dL is obtained from GSK standard units of $\mu\text{mol/L}$ as $CRT_{mg/dL} = 0.0113 \times CRT_{\mu\text{mol/L}}$.
 
 The CKD-EPI GFR will also be calculated using Cystatin C, as follows $133 \times \min(Scys/0.8, 1)^{-0.499} \times \max(Scys/0.8, 1)^{-1.328} \times 0.996^{Age} \times [0.932 \text{ if female}]$ 
Where Scys is serum cystatin C mg/Liter, \min indicates the minimum of Scr/0.8 or 1, and \max indicates the maximum of Scys/0.8 or 1.

Lab Toxicities – DAIDS Grading based on Version 2.1, March 2017, as specified in the protocol of Appendix 11.2.

 Toxicities will be based on the Division of AIDS (DAIDS) grading system, Version 2.1, March 2.17, as specified in the protocol of Appendix 11.2 Toxicity grades provided by the central laboratory do not distinguish between abnormally high or low criteria, when both are relevant for a parameter. When summarising toxicity grades for such parameters, they will be categorised as to whether they are above or below the midpoint of normal range.

Laboratory Parameters			
	Parameter	Below Midpoint for those ≥Grade 1	Above Midpoint for those ≥Grade 1
	Fasted glucose	Hypoglycemia	Hyperglycemia
	Sodium	Hyponatremia	Hypernatremia
	Potassium	Hypokalemia	Hyperkalemia
National Cholesterol Education Program (NCEP) Lipid Categories			

 In addition to DAIDS toxicity grades (see protocol), lipid values will be categorized according to the 2001 NCEP Adult Lipid Guidelines [Grundy, 2001] 			
Parameter	Value Range (mmol/L)	Value Range (mg/dL)	Category
Triglycerides	<1.70	<150	Normal
	1.70 to <2.26	150 to <200	Borderline High
	2.26 to <5.65	200 to <500	High
	≥5.65	≥500	Very High
Total Cholesterol	<5.18	<200	Desirable
	5.18 to <6.21	200 to <240	Borderline High
	≥6.21	≥240	High
HDL Cholesterol	<1.04	<40	Low
	1.04 to <1.56	40 to <60	Normal
	≥1.56	≥60	High
LDL Cholesterol	<2.59	<100	Optimal
	2.59 to <3.37	100 to <130	Near/Above Optimal
	3.37 to <4.14	130 to <160	Borderline High
	4.14 to <4.92	160 to <190	High
	≥4.92	≥190	Very High
Percentage change for lipids			

The percentage change from baseline is calculated as:
 $\% \text{ change from baseline} = \frac{\text{value at Week 48 or 96} - \text{baseline value}}{\text{baseline value}} \times 100\%$			
Total Cholesterol / HDL Cholesterol Ratio			

 When both total cholesterol and HDL cholesterol results are available from the same date for a participant, then the ratio will be calculated by dividing the total cholesterol result by the HDL cholesterol result. The ratio can be classified as follows: 			
	Parameter	Value Range	
	Total Cholesterol / HDL Ratio	< 3.5	
		3.5 to < 4.4	
		4.4 to < 5	
		≥ 5	
Other Safety Endpoints			
Corrected QT (QTc)			
When not entered directly in the eCRF, corrected QT intervals by Bazett's (QTcB) and Fridericia's			

Other Safety Endpoints

(QTcF) formulas will be calculated, in msec, depending on the availability of other measurements.

If RR interval (in msec) is provided then missing QTcB and/or QTcF will be derived as

$$QTcB = \frac{QT}{\sqrt{RR/1000}} \quad QTcF = \frac{QT}{\sqrt[3]{RR/1000}}$$

where uncorrected QT interval is also measured in msec.

If RR interval is not provided directly and one of QTcB or QTcF has been entered, then RR interval can be obtained from the above formulas and used to calculate the other correction method value; i.e.,

$$QTcB = \sqrt{\frac{QTcF^3}{QT}} \quad QTcF = \sqrt[3]{QT \cdot QTcB^2}$$

Extent of Exposure

- Exposure to CAB+RPV (oral lead-in or oral bridging) and CAB LA+RPV LA will be calculated from the IP eCRF pages.
- For Maintenance Phase:
 - Exposure to oral CAB+RPV (oral lead-in) = IP (oral lead-in) stop date - IP (oral lead-in) start date + 1
 - Exposure to CAB LA + RPV LA = Number of IP injections received during maintenance phase (up to but not including injections administered at Week 100)
 - Overall exposure to IP:
 - For participants on Q4W arm: min [Date of Latest Maintenance Phase Visit up to and including Week 100, max (Date of Last Injection + 35, Date of Last Dose of Oral CAB+RPV)] – min (Start Date for Oral lead-in CAB+RPV, Date of First Study Injection) + 1
 - For participants on Q8W arm: min [Date of Latest Maintenance Phase Visit up to and including Week 100, max (Date of Last Injection + 63, Date of Last Dose of Oral CAB+RPV)] – min (Start Date for Oral lead-in CAB+RPV, Date of First Study Injection) + 1
- For Maintenance + Extension Phase
 - Exposure to CAB LA + RPV LA = Number of IP injections received during Maintenance Phase + Extension Phase
 - Overall Exposure to IP:
 - For participants on Q4W arm: min [Date of Latest Visit, max (Date of Last Injection + 35, Date of Last Dose of Oral CAB+RPV)] – min (Start Date for Oral lead-in CAB+RPV, Date of First Study Injection) + 1
 - For participants on Q8W arm: min [Date of Latest Visit, max (Date of Last Injection + 63, Date of Last Dose of Oral CAB+RPV)] – min (Start Date for Oral lead-in CAB+RPV, Date of First Study Injection) + 1
- Last Injection and/or Last Dose of Oral CAB+RPV are only applicable to those who permanently discontinued study treatment.

Other Safety Endpoints

 • Duration of dosing in participant years will be calculated as the sum of participant duration of dosing in days (across all participants)/365.25 • Participants who were randomized but did not report a IP start date will be categorised as having zero days of exposure.
Adherence to CAB/RPV Injection Schedule

Timeliness of Injections relative to Date of Projected Dosing Visits are assessed by using "actual injection visit date - projected visit date from first injection". The injections of interest in adherence analysis are those after first injection. For participants requiring the oral CAB+RPV lead-in, the first injection is planned to be taken at Week 4B. For participants not requiring the oral CAB+RPV lead-in, the first injection is planned to be taken at Baseline/Day 1. Each injection visit is counted only once. Individual CAB and RPV injections administered at the same visit are not counted twice. "Extra" unscheduled injections are excluded from all derivations. For example, if during a scheduled visit a participant receives 1 ml of injection instead of 2 ml due to a dosing error, but this participant returns one week later for the remaining 1 ml injection, then the additional visit is excluded. If a participant receives an extra injection at an unscheduled visit by mistake, this visit will also be excluded.
 
The categories of Timeliness of Injections relative to Date of Projected Dosing Visits for summary are listed below:
 
 < -14 days -14 to -8 days -7 to -4 days -3 to -2 days -1 0 day 1 2 to 3 days 4 to 7 days 8 to 14 days >14 days Missed Injection without Oral Bridging Missed Injection with Oral Bridging
Columbia Suicide Severity Rating Scale (C-SSRS)

 • Missing data will not have any imputation performed (Nilsson et al, 2013).

